1.1. Study Objectives

The primary objective of this study is:

- To assess the efficacy of filgotinib, lanraplenib (GS-9876), and tirabrutinib (GS-4059) in adult subjects with active Sjogren's Syndrome (SjS)

The secondary objectives of this study are:

- To assess the safety and tolerability of filgotinib, lanraplenib, and tirabrutinib in active SjS
- To assess the effect of filgotinib, lanraplenib, and tirabrutinib on patient reported outcomes in active SjS

The exploratory objectives of this study are:

The logo for CCI (Clinical Care Innovations) is displayed in red text on a black rectangular background.

1.2. Study Design

This is a Phase 2, multicenter, randomized, double-blind, placebo-controlled study to evaluate the safety and efficacy of filgotinib, lanraplenib (GS-9876), and tirabrutinib (GS-4059) in adult male and female subjects with active SjS.

At Day 1, eligible subjects will be randomized 1:1:1:1 to daily oral filgotinib (200 mg), lanraplenib (30 mg), tirabrutinib (40 mg) or placebo to match (PTM). Randomization will be stratified by: use of concurrent immunomodulatory drugs at baseline (Y/N: conventional synthetic disease modifying antirheumatic drugs (csDMARD[s]) or corticosteroids), and the hematologic + biological component scores of the EULAR Sjogren's syndrome disease activity index (ESSDAI) obtained at screening (combined score of <2 or ≥ 2).

[figure not shown]
Stable medications at Day 1 should be continued during the study dosing period through Week 48. Dose adjustments for toxicities and dose adjustment of corticosteroids are allowed after Week 12. Subjects will return to the study site for scheduled study visits at Weeks 2, 4, 8, 12, 18, 24, 26, 28, 32, 36, 42, and 48 ([Appendix 1](#)).

At completion of the Week 24 visits, subjects on placebo will be re-randomized 1:1:1, in a blinded fashion, to daily oral filgotinib (200 mg), lanraplenib (30 mg), or tirabrutinib (40 mg) without further stratification. Dosing and assessments for all subjects will continue through Week 48.

CCI

Subjects who discontinue study drug for any reason (other than noncompliance) may continue to participate in scheduled study visits and procedures, as long as deemed medically appropriate by the investigator. Subjects who discontinue all study participation will have an early termination (ET) visit; these subjects, and those who complete the study, should return to the study site for a follow-up visit, 4 weeks after the last dose of study drug (subjects who have discontinued study drug \geq 4 weeks prior to the ET/Week 48 visit, do not need a follow up visit).

Figure 1. Study Design Schematic

1.3. Sample Size and Power

The sample size was estimated based on historical data. Assuming a response rate of 70% for an active arm and 30% for the placebo arm at Week 12, approximately 35 evaluable subjects will be needed in each arm to achieve 85% power to detect a significant difference at a 2-sided, 0.05-level. Enrollment of approximately 35 subjects per arm is planned to ensure that a sufficient number of subjects is available for the analysis of the primary endpoint.

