 - $\geq 20\%$ improvement in hsCRP
 - $\geq 20\%$ improvement in at least 3 out of 5 subject reported, SjS related visual analog scales (VAS; subject's assessment of global disease, pain, oral dryness, ocular dryness and fatigue)
 - no worsening (defined as > 30 mm increase from baseline) in any of the above VAS
- For subjects without elevated hsCRP (< 1.5 ULN of hsCRP) at Day 1, subjects are considered to be a responder if achieve all of the following:
 - no increase ≥ 1.5 ULN of hsCRP
 - $\geq 20\%$ improvement in at least 3 out of 5 subject reported, SjS related VAS (subject's assessment of global disease, pain, oral dryness, ocular dryness and fatigue)
 - no worsening (defined as > 30 mm increase from baseline) in any of the above VAS

Secondary endpoints include: the change in ESSDAI and in ESSPRI from baseline to Week 12 and 24

Pharmacokinetics:	Plasma concentrations of filgotinib (and its metabolite GS-829845), GS-9876, and GS-4059 will be listed and summarized using descriptive statistics.
--------------------------	--

Statistical Methods:

The primary analysis set for efficacy analyses will be the Full Analysis Set (FAS), which includes all randomized subjects who received at least one dose of study drug.

The primary endpoint is the proportion of subjects fulfilling response criteria as outlined above. The primary analysis will consist of a superiority test of each of filgotinib, GS-9876 or GS-4059 compared to placebo, respectively. Cochran Mantel Haenszel (CMH) approach adjusted for the randomization stratification factors will be used for the hypothesis testing at the 2-sided 0.05-level.

Based on results of prior SjS studies, assuming a response rate of 70% for the active arm and 30% for the placebo arm at Week 12, at least 35 evaluable subjects will be needed in each arm to achieve 85% power to detect a significant difference at a 2-sided, 0.05-level. Therefore, a total of approximately 140 subjects are planned to be enrolled in the study.

All continuous endpoints will be summarized using an 8-number summary (n, mean, standard deviation [SD], median, 1st quartile [Q1], 3rd quartile [Q3], minimum, maximum) by treatment group and by study part. All categorical endpoints will be summarized by the number and percentage of subjects who meet the endpoint definition.

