8.9. Sample Size

Based on results of prior SJS studies, assuming a response rate of 70% for an active arm and 30% for the placebo arm at Week 12, approximately 35 evaluable subjects will be needed in each arm to achieve 85% power to detect a significant difference at a 2-sided, 0.05-level. Enrollment of approximately 35 subjects per arm is planned to ensure that a sufficient number of subjects is available for analysis of the primary endpoint.

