6.3. Analysis for the Primary Efficacy Endpoint

6.3.1. Primary Analysis of Primary Endpoint

In the primary analysis, the primary outcome in each active treatment group will be compared to the outcome in the placebo group using a superiority test at the 2-sided 0.05-level. The following null hypotheses will be tested (vs. the respective alternative hypotheses):

- H01: There is no difference in the responder rate between filgotinib 200 mg group and placebo group at Week 12
- H02: There is no difference in the responder rate between lanraplenib 30 mg group and placebo group at Week 12
- H03: There is no difference in the responder rate between tirabrutinib 40 mg group and placebo group at Week 12

The analyses will be performed using Cochran Mantel Haenszel (CMH) test adjusted for the randomization stratification factors. If CMH test stratified by both stratification factors is not appropriate due to small cell counts then the levels of the stratification by ESSDAI scores will be pooled, and the analysis will be stratified only by use of concurrent immunomodulatory drugs at baseline. Each of the three hypotheses will be tested separately at the 2-sided, 0.05-level.

The primary analysis will be based on the Treatment Policy Estimand, with missing values imputed by multiple imputation method described in Section 6.1.

The number and percentage of responders in each treatment group as well as 95% confidence intervals (CIs) will be presented for each visit.

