10. SOFTWARE

SAS[®] Software Version 9.4. SAS Institute Inc., Cary, NC, USA.

nQuery Advisor(R) Version X.0. Statistical Solutions, Cork, Ireland.

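### The sample-size statement does not reproduce: at 70% vs 30% and 2-sided 0.05, 35 per arm gives about 92% power with the planned CMH test (88% by Fisher), not 85%

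*SAP*

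**What the plan says.** SAP 1.3 sets the design rates: "Assuming a response rate of 70% for an active arm and 30% for the placebo arm at Week 12". From these it concludes that "approximately 35 evaluable subjects will be needed in each arm to achieve 85% power to detect a significant difference at a 2-sided, 0.05-level". Protocol 8.9 has the same sentence ("approximately 35 evaluable subjects will be needed in each arm to achieve 85% power"). The Synopsis (Statistical Methods) makes 35 a minimum rather than an approximation: "at least 35 evaluable subjects will be needed in each arm to achieve 85% power to detect a significant difference".

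On enrolment, SAP 1.3 continues: "Enrollment of approximately 35 subjects per arm is planned to ensure that a sufficient number of subjects is available". Protocol 8.9 says the same, so the number to enrol equals the number called evaluable.

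None of the three passages names the test or formula behind the calculation. The planned primary analysis is in SAP 6.3.1: "The analyses will be performed using Cochran Mantel Haenszel (CMH) test adjusted for the randomization stratification factors", each hypothesis at 2-sided 0.05. SAP 3.5 rules out any multiplicity adjustment. SAP 10 lists the sample-size software as "nQuery Advisor(R) Version X.0".

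**The concern.** The statement gives everything needed to check it: two rates, a level, a power and a number per arm, with 1:1 allocation for each comparison. A 40-point difference around 50% is large, and 35 per arm looks like more than 85% power requires.

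The direction of the error matters. Too few subjects would threaten the primary comparison, and that is not the case here. What is at stake is whether the reported power is true, whether a reader can see how much attrition the design tolerates, and whether 35 came from an alpha or effect size other than the one documented. The true power also bears on how informative a negative result for one of the three drugs would be.

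**Working it through.** **Inputs.** p1 = 0.70, p2 = 0.30, 2-sided alpha = 0.05, power 0.85, 35 evaluable per arm (SAP 1.3; Protocol 8.9; Synopsis). Allocation 1:1:1:1 (SAP 1.2). No alpha adjustment (SAP 3.5, 6.3.1). Primary test: CMH over two binary factors, so four strata (SAP 3.3, 6.3.1).

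**Attempt to reproduce 35.** Pooled normal-approximation (chi-square) formula:

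n = [z(0.975)·√(2·0.5·0.5) + z(0.85)·√(0.21 + 0.21)]² / 0.4²

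= [1.960·0.7071 + 1.036·0.6481]² / 0.16 = 26.46, so **27 per arm**.

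The continuity correction gives n = (26.46/4)·[1 + √(1 + 4/(26.46·0.4))]² = 31.26, so **32 per arm**.

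Other variants move further away: arcsine 26.51 (27), unpooled variance 24, one-sided 0.05 22 (26 with continuity correction). None gives 35.

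**Power at 35 per arm, same formula.** z = (0.4·√35 − 1.960·0.7071)/0.6481 = 1.51, so power is 93.5%.

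**Exact enumeration and simulation.** The CMH figures come from 200,000 simulated trials per setting, without continuity correction, with 70% and 30% in every stratum. The documents do not give stratum shares. The four-stratum runs assumed 25/25/25/25, 10/20/30/40 and 40/40/10/10; the two-stratum run (the SAP's pooling fallback) assumed 50/50.

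| Method | Around the 85% threshold | n for 85% | Power at 35 |
|---|---|---|---|
| Chi-square, formula | 26.46 | 27 | 93.5% |
| Chi-square, exact | 27: 84.0%; 28: 86.1% | 28 | 92.4% |
| CMH, four strata, simulated | 28: 84.9%; 29: 86.2–86.3% | 29 | 92.1% |
| CMH, two strata, simulated | 27: 84.4%; 28: 86.2% | 28 | 92.6% |
| Fisher, exact | 30: 83.8%; 31: 86.0% | 31 | 88.2% |
| Continuity-corrected, formula | 31.26 | 32 | 89.5% |

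The Yates-corrected chi-square test, enumerated exactly, also gives 88.2% at 35. Exact power does not rise smoothly with n: the uncorrected chi-square test gives 85.95% at 25, then drops below 85% at 26 and 27. The exact entries are the n from which power stays above 85% over the range checked (25 to 36).

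**Gap.** The nearest method on n is the continuity-corrected formula (35 − 32 = 3 subjects). The nearest on power is Fisher (88.2 − 85 = 3.2 points). For the planned four-stratum CMH the gaps are 35 − 29 = 6 subjects and 92.1 − 85 = 7.1 points. The largest power gap is 93.5 − 85 = 8.5 points.

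**Margin if 35 are enrolled.** 35 − 27 = 8 (23%) by the chi-square formula; 35 − 29 = 6 (17%) by CMH; 35 − 31 = 4 (11%) by Fisher; 35 − 32 = 3 (9%) by the continuity-corrected formula.

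**What would give 35.** With the uncorrected formula, 65% vs 30% at 0.05 gives 85.0% at 35 per arm. So does 70% vs 35%, its mirror image. Keeping 70% vs 30% but setting alpha to 0.05/3 = 0.0167 gives n = 34.94 and 85.1% at 35. The documents state none of these, and SAP 3.5 and 6.3.1 exclude the adjusted alpha as the level of testing. An attrition allowance of 20% on 28 (28/0.8 = 35), or 8% on 32 (32/0.92 = 34.8), would also give 35, but the text calls the 35 evaluable.

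**The case against.** The strongest reply is that nothing is broken. Thirty-five per arm delivers at least 85% power by every method in the table, the sample size, alpha and analysis need no change, and two of the three passages say only approximately 35. A planner using Fisher's test would be 4 subjects and 3.2 points away. Since no planning test is named, 92% reflects a choice of test.

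The conservative direction is accepted, and it limits the consequence. It does not make the sentence correct: the number described as needed for 85% power is not, by any standard method tried, and the Synopsis states it as a minimum. Taking the planned test as the reference is a reasonable choice, and Fisher's figure is reported beside it.

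Two technical cautions stand. The CMH figures assume the same rates in every stratum and complete data. The primary analysis uses the Full Analysis Set with multiple imputation (SAP 6.1, 6.3.1), so a subject without Week 12 data is imputed rather than dropped, and power would be somewhat below the complete-data figure. The margin of 3 to 8 is therefore a guide to information loss, not a count of subjects who would leave the analysis. Also, 27 comes from the approximation; exact chi-square power at 27 is 84.0%.

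The inputs that would give 35 are conjecture. They show only that the origin cannot be determined from the documents. The software version is a separate editorial gap, and filling it would not by itself identify the test.

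**Conclusion.** The concern holds. The stated rates, level, power and number per arm are inconsistent in all three places where they appear. At 70% vs 30% and 2-sided 0.05, 85% power needs 27 to 32 evaluable subjects per arm depending on the test. Thirty-five gives about 92% with the planned CMH test and 88.2% with Fisher's.

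Read the other way, 35 per arm at 0.05 gives 85% power for an active rate of about 65% (normal approximation) or 66% (exact chi-square, 85.7%), not 70%.

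No other section explains the figure. Attrition does not, because the evaluable number and planned enrolment are the same; multiplicity does not, because the SAP excludes adjustment. This is a reporting error that should be corrected. It is not a design failure.

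**What to change.** In the Synopsis, Protocol 8.9 and SAP 1.3, name the test used and give one consistent statement, for example:

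> With 35 evaluable subjects per arm, power is about 92% (CMH or chi-square test; 88% by Fisher's exact test) at 2-sided 0.05 for response rates of 70% and 30%. About 27 to 32 evaluable subjects per arm, depending on the test, suffice for 85% power, so enrolling 35 allows for about 3 to 8 non-evaluable subjects per arm.

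Add that the CMH figure assumes equal rates across strata and complete data. Settle on either a minimum or an approximate 35 throughout.

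If 35 was derived from another response rate or alpha, state that input instead; if it was alpha, reconcile it with SAP 3.5 and 6.3.1. Fill in the software version in SAP 10.

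The cost is wording in three places and one version number. Sample size, alpha and analysis are unchanged.

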2. TYPE OF PLANNED ANALYSIS

2.1. Interim Analyses

An external data monitoring committee (DMC) has not been established for this study. Therefore, no analyses will be conducted for the external DMC.

2.2. Internal Data Monitoring

To assess the safety and efficacy of filgotinib, lanraplenib and tirabrutinib, and for further planning and development of these products, a Gilead internal unblinded team independent of the blinded study team will be assembled. This group will consist of at least one representative from Clinical Research, Biostatistics, and Pharmacovigilance/Epidemiology, and may include other personnel as necessary. The Gilead internal unblinded team will be granted access to unblinded clinical data including treatment assignments to closely monitor study progress and drug safety. The activities of the internal unblinded data monitoring team will be governed by the team Charter.

To mitigate the risks of inadvertently releasing the treatment information to the sites and subjects, the internal team will keep the unblinded information confidential and will not communicate the information to the blinded study team, site staff or subjects. Data unblinding due to medical emergency will follow standard Gilead procedures.

2.3. Primary (Week 24) Analysis

A planned Week 24 analysis will be conducted after all subjects have either completed their Week 24 visit or prematurely discontinued from the study.

A pre-specified sponsor team (members are not actively involved in the conduct of the study) will review the Week 24 unblinded safety and efficacy analysis results. A memo and a list will be maintained which documents the individuals granted access to the Week 24 unblinded results along with the justification for unblinding in accordance with Gilead SOPs. The Interim Analysis Data Integrity and Communication Plan will be developed prior to unblinding. The Study Management Team members with direct involvement in the conduct of the study will remain blinded to treatment assignments throughout the trial, until all subjects have completed all planned study visits and the database has been locked.

All planned analyses of the placebo-controlled period described in this SAP will be provided to the Designated Unblinded Study Team (see the Interim Analysis Data Integrity and Communication Plan) and will contain individual subject treatment assignments.

The following primary and secondary analysis reports and summaries may be provided to the project planning team (specified Gilead executives and the designated study team members):

- Demographic characteristics (only Total column - all treatment groups combined)
- Baseline characteristics (only Total column)

- Disposition (only Total column)
- Primary Responder Analysis at Week 12
- Inferential analysis of ESSDAI Change from Baseline to Week 12 and Week 24
- Inferential analysis of EULAR Sjögren's Syndrome Patient Reported Index (ESSPRI) Change from Baseline to Week 12 and Week 24
- Other analyses as deemed necessary for program planning purposes

These reports will contain unblinded treatment group level information (not the individual subject treatment assignments).

2.4. Final Analysis

After all subjects have completed the study, outstanding data queries have been resolved or adjudicated as unresolvable, and the data have been cleaned and finalized, the study blind will be broken and the final analysis of the data will be performed.

3. GENERAL CONSIDERATIONS FOR DATA ANALYSES

Analysis results will be presented using descriptive statistics. For categorical variables, the number and percentage of subjects in each category will be presented; for continuous variables, the number of subjects (n), mean, standard deviation (SD), median, first quartile (Q1), third quartile (Q3), minimum, and maximum will be presented.

All statistical tests will be 2-sided and performed at the 0.05 significance level unless otherwise specified.

By-subject listings will be presented for all subjects in the All Randomized Analysis Set and sorted by subject ID number, visit date, and time (if applicable). Data collected on log forms, such as AEs, will be presented in chronological order within the subject. The treatment group to which subjects were initially assigned will be used in the listings. Age, sex at birth, race, and ethnicity will be included in the listings, as space permits.

3.1. Analysis Sets

Analysis sets define the subjects to be included in an analysis. Analysis sets and their definitions are provided in this section. Subjects included in each analysis set will be determined before the study blind is broken for analysis. The analysis set will be identified and included as a subtitle of each table, figure, and listing.

For each analysis set, the number and percentage of subjects eligible for inclusion, as well as the number and percentage of subjects who were excluded and the reasons for their exclusion, will be summarized by treatment group.

A listing of reasons for exclusion from analysis sets will be provided by subject.

3.1.1. All Randomized Analysis Set

All Randomized Analysis Set includes all subjects who were randomized in the study. This is the primary analysis set for by subject listings.

3.1.2. Full Analysis Set

The primary analysis set for efficacy analyses will be the Full Analysis Set (FAS), which includes all randomized subjects who received at least one dose of study drug.

3.1.3. Safety Analysis Set

The primary analysis set for safety analyses will be the Safety Analysis Set, which includes all subjects who received at least one dose of study drug.

3.1.4. Per-Protocol Analysis Set

No analyses will be performed using the Per-Protocol analysis set.

3.1.5. Pharmacokinetic Analysis Set

The Pharmacokinetic (PK) Analysis Set will include all subjects in the Safety Analysis Set who have at least 1 non-missing post-dose PK concentration data for filgotinib, lanraplenib, tirabrutinib, and/or their metabolite(s). This is the primary analysis set for all PK analyses.

3.1.6. PK Substudy Analysis Set

CCI [REDACTED]

3.1.7. Biomarker Analysis Set

The primary analysis set for biomarker analyses will be the Biomarker Analysis Set, which includes all randomized subjects who received at least one dose of study drug and have at least one evaluable measurement available at any time point for a given biomarker of interest.

3.2. Subject Grouping

For the analysis of placebo-controlled period (up to week 24), subjects will be presented by four treatment groups:

- Filgotinib 200 mg
- Lanraplenib 30 mg
- Tirabrutinib 40 mg
- Placebo

For the analyses of the entire study period, subjects will be grouped into seven treatment groups as specified in Table 1. For the analyses based on the FAS Analysis Set, subjects will be grouped according to the treatment to which they were randomized at Study Day 1 and Week 24. For the analyses based on the Safety Analysis Set, subjects will be grouped according to the actual treatment that they received. The actual treatment received will differ from the randomized treatment only when their actual treatment differs from randomized treatment for the entire treatment duration.

Table 1. Treatment Groups for the Entire Study Summaries

Filgotinib 200 mg	Filgotinib 200 mg from Study Day 1
Lanraplenib 30 mg	Lanraplenib 30 mg from Study Day 1
Tirabrutinib 40 mg	Tirabrutinib 40 mg from Study Day 1
Placebo/Filgotinib 200 mg	Placebo up to Week 24 and Filgotinib 200 mg after Week 24 first dose
Placebo/Lanraplenib 30 mg	Placebo up to Week 24 and Lanraplenib 30 mg after Week 24 first dose
Placebo/Tirabrutinib 40 mg	Placebo up to Week 24 and Tirabrutinib 40 mg after Week 24 first dose
Placebo	Placebo group with study drug withdrawn prior to or at Week 24 (not received drug assigned at Week 24)

For the PK Analysis Set, subjects will be grouped according to the actual treatment they received.

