3.2. Study Treatments

Following completion of screening assessments, eligible subjects will be randomized 1:1:1:1 in a blinded fashion to active investigational product or PTM:

- **Filgotinib 200 mg arm (n=35): filgotinib (1 x 200 mg tablet once daily) + PTM GS-9876 (1 x tablet once daily) + PTM GS-4059 (1 x tablet once daily)**
- **GS-9876 30 mg arm (n=35): PTM filgotinib (1 x tablet once daily) + GS-9876 (1 x 30 mg tablet once daily) + PTM GS-4059 (1 x tablets once daily)**
- **GS-4059 40 mg arm (n=35): PTM filgotinib (1 x tablet once daily) + PTM GS-9876 (1 x tablet once daily) + GS-4059 (1 x 40 mg tablet once daily)**
- **Placebo arm (n=35): PTM filgotinib (1 x tablet once daily) + PTM GS-9876 (1 x tablet once daily) + PTM GS-4059 (1 x tablet once daily)**

Randomization will be stratified by use of concurrent immunomodulatory drugs at baseline (Y/N: csDMARDs or corticosteroids), and the hematologic + biological component scores of the ESSDAI obtained at screening (combined score of <2 or ≥ 2).

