7. SAFETY ANALYSES

The safety analyses will be performed for the placebo-controlled treatment period up to Week 24, and for the entire study duration. Analyses for these periods will be presented by the treatment groups specified in Section 3.

For the analyses of adverse events (AEs) that include data after Week 24 the exposure-adjusted analyses will be presented.

For the AEs, laboratory results and concomitant medication data, the collection/start date will be used to determine which reporting period the record belongs to. For other parameters collected on CRFs, the nominal visits will be used.

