7.1.6. Summaries of Adverse Events and Deaths

TEAEs will be summarized based on the Safety Analysis Set.

The tables will be presented by treatment period: placebo-controlled period (up to Week 24) and active treatment period. The overall summary of TEAEs will also be provided for the entire study duration.

The number and percentage of subjects who experienced at least 1 TEAE will be provided and summarized by SOC, HLT, PT, and treatment group. For other AEs described below, summaries will be provided by SOC, PT, and treatment group:

- All TEAEs
- TEAEs of Grade 3 or higher (by maximum severity)
- All TE treatment-related AEs
- TE treatment-related AEs of Grade 3 or higher (by maximum severity)
- All TE SAEs
- All TE treatment-related SAEs
- All TEAEs leading to premature discontinuation of study drug
- All TEAEs leading to premature discontinuation of study
- All TEAEs leading to death (i.e. outcome of death)

A brief, high-level summary of AEs described above will be provided by treatment group and by the number and percentage of subjects who experienced the above AEs. All deaths observed in the study will also be included in this summary.

Multiple events will be counted only once per subject in each summary. Adverse events will be summarized and listed first in alphabetic order of SOC and HLT within each SOC (if applicable), and then by PT in descending order of total frequency within each SOC. For summaries by severity grade, the most severe grade will be used for those AEs that occurred more than once in an individual subject during the study.

In addition to the above summary tables, all TEAEs and TE treatment-related AEs will be summarized by PT only, in descending order of total frequency.

The data listings will be provided for the following:

- All AEs, indicating whether the event is treatment emergent

- All AEs of Grade 3 or higher
- SAEs
- Deaths
- AEs leading to premature discontinuation of study drug
- AEs leading to premature discontinuation of study

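### In entire-study summaries the 'Placebo' column holds only placebo subjects who stopped by Week 24, so its discontinuation figures are inflated and it is not a randomised comparator

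*SAP*

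**What the plan says.** SAP 3.2 sets two groupings. Up to Week 24: "For the analysis of placebo-controlled period (up to week 24), subjects will be presented by four treatment groups", with the whole placebo arm in one column. Beyond that: "For the analyses of the entire study period, subjects will be grouped into seven treatment groups as specified in Table 1".

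In Table 1 the three active columns contain everyone on that drug from Day 1. Placebo subjects who go on to active drug are split by destination, for example "Placebo up to Week 24 and Filgotinib 200 mg after Week 24 first dose". The column labelled simply 'Placebo' is what remains: "Placebo group with study drug withdrawn prior to or at Week 24 (not received drug assigned at Week 24".

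These outputs draw on the seven groups:

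- SAP 7 presents the placebo-controlled and entire-study safety analyses by the Section 3 groups and adds: "For the analyses of adverse events (AEs) that include data after Week 24 the exposure-adjusted analyses will be presented".
- SAP 7.1.6 lists events leading to discontinuation of study drug among its categories and states: "The overall summary of TEAEs will also be provided for the entire study duration".
- SAP 4.1 gives disposition for the whole study, with each column's own Safety Analysis Set as denominator.
- SAP 7.2.2.3 and 7.2.3 give laboratory and liver abnormalities for the entire study.
- SAP 6 evaluates efficacy up to Week 48.

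No section tells the reader that the 'Placebo' column is a selected subset.

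**The concern.** Membership of the 'Placebo' column depends on something that happens after randomisation, stopping study drug, and this is done to one arm only. The column then sits beside three active columns formed by assignment. A reader of the whole-study overview would naturally compare across the row, and for discontinuation that comparison is distorted in a known direction.

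The Placebo/active columns have the opposite problem. They hold only subjects who reached Week 24 and took the new drug, so no permanent discontinuation during the placebo phase can appear there. Because SAP 7.1.5.1 counts whole-study treatment-emergent events from the start of any study drug, these columns also mix placebo-time and active-time events under a heading that names an active drug. No whole-study column shows what happened to the placebo arm as a whole.

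**Working it through.** The documents state no figure for this point, so there is nothing to reproduce.

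**Inputs**

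- N = 35, the planned placebo arm (Protocol 3.2).
- Completers contribute 24 weeks of placebo time (SAP 1.2).
- w, the number of placebo subjects who stop by Week 24 or do not take the Week 24 drug: not given. Assumed range 2 to 18, that is 2/35 = 5.7% to 18/35 = 51.4%.
- e, mean weeks of counted time per stopper: not given. Assumed 12, with 6 to 18 as a check.
- x, events leading to discontinuation of placebo by Week 24: assumed 2 for illustration. It cancels from the ratios.

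**Discontinuation.** Everyone in the column has stopped study drug, so the column shows w/w = 100%. The whole arm shows w/35.

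**Events leading to discontinuation, crude.** All x events fall among the stoppers. The column shows x/w and the whole arm x/35 (2/35 = 5.7%), so the inflation is 35/w for any x.

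**Exposure-adjusted.** The numerator is again the same, so the inflation is the ratio of person-time:

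[(35 − w) × 24 + w × e] / (w × e)

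This exceeds 35/w whenever e is below 24 weeks. SAP 4.2.1 defines duration of exposure, but Section 7 does not say whether that is the denominator or whether the 30 days after the last dose count. The table shows both, the second with e = 12 + 30/7 = 16.3 weeks.

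| w | Discontinued, whole arm | x = 2: column shows | Crude inflation 35/w | Exposure-adjusted, e = 12 | Exposure-adjusted, e = 16.3 |
|---|---|---|---|---|---|
| 2 | 5.7% | 100% | 17.5 | 34.0 | 25.3 |
| 4 | 11.4% | 50.0% | 8.75 | 16.5 | 12.4 |
| 7 | 20.0% | 28.6% | 5.0 | 9.0 | 6.9 |
| 11 | 31.4% | 18.2% | 3.2 | 5.4 | 4.2 |
| 18 | 51.4% | 11.1% | 1.9 | 2.9 | 2.4 |

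Example for w = 4, e = 12: (31 × 24 + 48)/48 = 792/48 = 16.5. With w = 4, moving e from 6 to 18 weeks moves the result from 768/24 = 32.0 to 816/72 = 11.3.

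**Other adverse events.** The ratio does not carry over. Stoppers may have had more events, but they also had at most about 24 weeks on drug plus 30 days, against up to 48 weeks on active drug. A crude percentage could be too high or too low.

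**By-visit efficacy.** Subjects who stop drug may keep attending (Protocol 3.1). After Week 24, 'Placebo' values therefore come only from off-drug stoppers who still attend. The direction of any bias cannot be derived from the documents.

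**A conflict within SAP 3.2.** The Full Analysis Set rule groups subjects by randomisation at Day 1 and Week 24. Table 1 puts a subject who is re-randomised but never takes the new drug under 'Placebo'.

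**The case against.** The strongest reply is that the valid comparison is already planned in the same section. The four-group tables keep the whole placebo arm to Week 24, and every primary and secondary endpoint falls at Week 12 or 24. Adverse-event tables are split into placebo-controlled and active-treatment periods, with only the overall summary added for the entire study. Disposition is also shown by period. SAP 7.1.5.1 already separates events up to Week 24 from those on active treatment, and SAP 7.2 re-baselines switchers. Table 1 then serves a view by treatment sequence in which each subject appears once, its row text says who is in the column, and the SAP never calls it a comparator.

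All of that stands and limits the reach of the point. It does not remove it: the whole-study overview, disposition and laboratory tables still print a column called 'Placebo' beside three complete arms.

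A reader might go further and infer that active drugs will look safer and more effective than placebo by construction. The documents do not support this beyond discontinuation and the events that cause it. Nor do they show why subjects would stop: Protocol 3.4.2 also lists subject request, noncompliance and investigator discretion.

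A reader might also settle on one large multiple. With 5 stoppers at a mean of 10 weeks, dosing time gives (30 × 24 + 50)/50 = 15.4-fold. Adding 30 days per stopper gives (720 + 71.4)/71.4 = 11.1-fold. Neither can be derived from the SAP, which gives no withdrawal rate and no person-time rule.

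**Conclusion.** The point holds for the entire-study outputs. Discontinuation under 'Placebo' is 100% whatever the data. The crude rate of events leading to it is overstated by 35/w: at least 3-fold if no more than about a third of the arm stops, and about 2-fold if half does. Exposure adjustment does not cure this, and it enlarges the inflation when stoppers' mean counted time is under 24 weeks. These sizes rest on the planned arm of 35 and on assumed values of w and e. For other adverse events and for efficacy the finding is only that the column is a selected subset, with bias possible in either direction. The primary and secondary analyses and the tables up to Week 24 are sound on this point, and laboratory and other safety summaries are descriptive. The change should be made, but no planned inference depends on it.

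**What to change.** For whole-study safety summaries, rewrite Table 1 as follows:

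- 'Placebo': all subjects treated with placebo, counting placebo time only, to the day before first active dose or, if not switched, to last dose + 30 days.
- The three Placebo/active columns: from first active dose only.
- Assign events and person-years by treatment at onset, and state the person-time denominator in SAP 7.
- Read comparisons from exposure-adjusted rates, because placebo time ends around Week 24 while active time runs to Week 48.

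Lay out disposition in the same way, so that the placebo arm's discontinuations have the whole arm as denominator.

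For Full Analysis Set by-visit efficacy displays, keep the randomised sequence. Rename the residual column, for example 'Placebo, not switched', footnote that it is not a randomised comparator, and reconcile Table 1 with the Full Analysis Set rule for subjects re-randomised but not dosed.

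The cost is new table wording and a treatment-at-onset flag. No new data are needed, because the date of first active dose is on the CRF (SAP 3.8.1). The downside is that switchers appear in two safety columns, which a footnote should say.
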